10.2.3.3 Acute vascular leak syndrome

High dose IL2 can induce a capillary leak syndrome and sepsis-like physiology (decreased systemic vascular resistance, increased cardiac output and some degree of peripheral or pulmonary interstitial edema and/or ascites). Cardiovascular toxicity may be additive when IL2 is combined with hu14.18. For Grade 3 acute vascular leak syndrome, see dose modification guidelines in Section 10.1

10.2.3.4 Dyspnea

Subjects experiencing dyspnea and whose oxygen saturation is less than 90% may receive brief oxygen supplementation. Subjects who experience this toxicity are often fluid overloaded and will need furosemide, provided that they are not hypotensive (see management of hypotension, above). Therapy will be discontinued and not restarted until the oxygen saturation is above 90% without oxygen supplementation. Once the oxygen saturation is above 90% without oxygen supplementation, treatment with hu14.18-IL2 may be reinitiated on the following day (if scheduled) at 100% dose (if recovery occurred in less than 1 hour) or at 50% reduced dose (if recovery took longer than 1 hour to resolve). If they are fluid overloaded, hypoxic and hypotensive, treatment should be stopped and vasopressor support initiated, as needed. Once toxicities resolve, subsequent treatment will be at the 50% dose level.

If dyspnea with oxygen saturation below 90% is recurrent, treatment will be stopped and patients managed as outlined above in this section. Treatment can be restarted (at their next scheduled infusion day) at 50% of the prior dose, if oxygenation is responsive to the management described above. If dyspnea with oxygen saturation below 90% is recurrent at 25% of the initial dose, treatment will be discontinued and the patient will be off protocol therapy.

If the oxygen saturation does not then improve to over 90% off of oxygen supplementation within 24 hours, treatment will be discontinued and restarted at 50% of the previous dose of

hu14.18-IL2, provided that the toxicity resolves. If they are fluid overloaded, hypoxic and hypotensive, treatment should be stopped and vasopressor support initiated, as needed. Once toxicities resolve, subsequent treatment will be at the 50% dose level.

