1.3.5 Human experience with hu14.18-IL2

The initial Phase I protocol for hu14.18-IL2 (designated EMD 273063, by EMD Serono, Inc., Rockland, MA, formerly by EMD Pharmaceuticals, Inc., Durham, NC, the sponsor of that trial) entitled Phase I/Ib Trial of the EMD 273063 Fusion Protein in subjects with GD2+ tumors (CO 98901), was initiated in September 1998 at the University of Wisconsin, Madison and treatment was completed in March 2002 (38). A total of 33 subjects with melanoma were enrolled to establish the MTD. Subjects were enrolled in cohorts of 3 or 6 subjects and administered hu14.18-IL2 at one of the following dose levels: 0.8, 1.6, 3.2, 4.8, 6.0 or 7.5 mg/m²/day. Hu14.18-IL2 was administered as a 4-hour IV infusion over 3 consecutive days during the first week of each course. Subjects with tumor regression or stable disease were given a second

course of treatment with hu14.18-IL2 four weeks after Course 1. Thirty-one subjects completed one course of treatment with hu14.18-IL2, and 19 subjects had stable disease following Course 1 and proceeded to receive a second course of treatment. The dose of 7.5 mg/m²/day was found to be the MTD, as 2 of 6 subjects showed reversible dose-limiting toxicity at this dose level (Table 1).

Table 1.
Dose-Limiting Toxicities Observed During Course 1 in Subjects Receiving HU14.18-IL2

Dose (mg/m²)	Total Subjects	Dose-Limiting Toxicity (number of subjects)
0.8	3	None
1.6	6	AST (1)¹
3.2	6	Hyperglycemia (2)²
4.8	6	Hypophosphatemia (4)³, Thrombocytopenia (1)
6.0	6	Hypoxia (1), Hypophosphatemia (3)³
7.5⁵	6	Hypoxia (1), AST/ALT (1)⁴, Hypotension (1), Hyperglycemia (1), Hypophosphatemia (3)³

¹ Grade 3 elevation of aspartate aminotransferase (AST).

² Subjects with known diabetes mellitus. The protocol was amended to exclude subjects with a known history of diabetes mellitus as this therapy may alter blood glucose levels.

³ Protocol amended to exclude grade 3 hypophosphatemia as a dose-limiting toxicity.

⁴ Grade 3 elevation of AST and alanine aminotransferase (ALT).

⁵ The dose of 7.5 mg/m²/day was found to be the MTD, as 2 of 6 subjects showed reversible dose-limiting toxicity at this dose level.

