Overall, hu14.18-IL2 was well tolerated, with most subjects experiencing mild to moderate adverse events (AEs), mainly known IL-2 side effects. Ten of 33 subjects (course 1) and 6 of 19 subjects (course 2) experienced pain related to the hu14.18-IL2 infusion that required opioids for pain management. Treatment related Grade 3 toxicities included hypotension (2 subjects; one subject did not require pressors), hypophosphatemia (11 subjects), hyperglycemia (3 subjects, 2 with known diabetes), transient hypoxia (3 subjects), aspartate aminotransferase elevation (2 subjects), hyper-bilirubinemia (1 subject) and transient fever >40° C (1 subject). No Grade 4 toxicities were observed. Adverse events are summarized in table 2 and 3 on page 16 and 17. Reversible Grade 3 hypotension was only seen in the 7.5 mg/m² dose level and was the toxicity that primarily defined the MTD.

Laboratory analyses showed lymphocytosis, expansion of CD16+ and CD56+ NK cells, marked peripheral lymphocyte activation (evidenced by a dose-dependent elevation of circulating sIL2R alpha chain), and enhanced ability of peripheral blood mononuclear cells (PBMC) to mediate GD2+ tumor cell killing through ADCC. Thus hu14.18-IL2 has demonstrated biological activities. PK results indicate the serum t_{1/2} of hu14.18-IL2 to be 3.7 hours.

Table 2. Adverse Events Observed with Hu14.18-IL2

Adverse Event ¹	Dose (mg/m ²) (course 1/course2)					
	0.8	1.6	3.2	4.8	6.0	7.5
Total Number of Subjects	3/2	6/6	6/1	6/5	6/3	6/2
Fever²						
39.1- 40 °C	1/0	2/1	0/0	1/3	5/0	4/1
> 40°C	0/0	0/0	0/0	0/0	0/0	0/0
Rigors or Chills (requiring opioids)	2/1	3/2	3/0	2/2	4/1	2/0
Hypotension						
Grade 2	0/0	0/0	1/0	3/3	2/1	1/0
Grade 3	0/0	0/0	0/0	0/0	0/0	1/1 ³
Transient hypoxia (grade 3)	0/0	0/0	0/0	0/0	1/0	0/1
Pruritis (grade 2)	0/1	1/4	2/0	3/3	3/2	2/1
Severe allergic reaction	0/0	0/0	0/0	0/0	0/0	0/0
Pain²						
Requiring opioids	0/0	1/3	0/0	3/1	2/1	4/1
Uncontrolled with opioids	0/0	0/0	0/0	0/0	0/0	0/0
Objective peripheral neuropathy	0/0	0/0	0/0	0/0	0/0	0/0
Decline in ECOG⁴ performance status >2	0/0	1/0	1/0	3/1	2/1	0/0

¹ Adverse events (all grade 3 and clinically significant grade 2 events) for all subjects for all courses were graded as defined by the NCI Common Toxicity Criteria unless otherwise indicated.

² Fever and pain were graded as defined by the University of Wisconsin Comprehensive Cancer Center Biologic Toxicity Criteria.

³ Subject did not require vasopressors.

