- If responsive (i.e., blood pressure increases to a systolic blood pressure over 100 mm Hg or to the patient's blood pressure prior to administration of hu14.18-IL2 for that day if the baseline systolic blood pressure was less than 100 mm Hg and no longer requiring vasopressor support), may reinitiate the following day (if scheduled) at 50% reduced dose. If hypotension is recurrent, treatment will be stopped and patients managed as outlined above in this section. Treatment can be restarted (at their next scheduled infusion day) at 25% of the initial dose, if systolic blood pressure is responsive to the fluid management described above. If hypotension is recurrent at this 25% dose, treatment will be discontinued and the patient will be off protocol therapy.
- For Grade 3 hypotension, see dose modification guidelines in section 10.1
- Additional boluses of 500 ml IV Normal Saline can be administered as clinically indicated

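### Section 10.2.3.4 allows a full-dose restart after brief desaturation with no grade limit, while the DLT rules require 50% if the event is Grade 3

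*Combined protocol and SAP*

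**What the plan says.** **Hypoxia rule.** Section 10.2.3.4 covers dyspnea with saturation below 90%. Once saturation is above 90% off oxygen, treatment "may be reinitiated on the following day (if scheduled) at 100% dose (if recovery occurred in less than 1 hour"). When recovery takes more than an hour, the restart is at half dose. No toxicity grade is mentioned.

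**Neighbouring rules.** The two sections just before it do separate out Grade 3. Section 10.2.3.2.2 says "For Grade 3 hypotension, see dose modification guidelines in section 10.1", and Section 10.2.3.3 says "For Grade 3 acute vascular leak syndrome, see dose modification guidelines in Section 10.1".

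**DLT rules.** Section 5.4.1 makes any Grade 3 or 4 CTCAE v3.0 toxicity a DLT unless it is listed in 5.4.3. None of the exceptions (a) to (j) in 5.4.3 names hypoxia or dyspnea. The closing paragraph of 5.4.3 requires any dose given after a DLT to be reduced. Footnote 4 to Figure 1 sets 50% of the starting dose at the first DLT, 25% at the second, and a stop at the third. Section 10.1.1 repeats the 50% for a same-course restart and adds case-by-case FDA contact. Section 5.4.4 makes reductions permanent.

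**Grade 4 rules.** Section 5.4.4.1 allows 50% after a short list of Grade 4 events, including fatigue lasting under 2 days once eligibility criteria are met. It withdraws subjects with any other treatment-related Grade 4 toxicity. Section 10.2.6 lets the next cycle restart at 50% after Grade 4 fatigue if performance status is 2 or better in under a week. Section 10.2.4 sets 50% for later courses after neurotoxicity of Grade 3 or higher lasting more than 3 days.

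**The concern.** A clinician managing a desaturation will open Section 10.2.3.4, which gives a complete instruction and no reason to look further. If the event was Grade 3, that instruction is full dose the next day. The DLT rules instead require a permanent reduction and contact with the FDA before resuming. At stake is a repeat of the full dose after a dose-limiting respiratory event, with a required regulatory step missed. Section 9.4.9 classes toxicity needing ventilatory support as unacceptable and pauses accrual when it occurs, so the plan itself treats respiratory toxicity as serious.

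The fatigue rules raise a lesser version of the same problem: one section permits treatment of a subject whom another withdraws.

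**Working it through.** The plan states no figure for this point, so there is none to reproduce. The check sets the rules side by side and adds simple dose arithmetic.

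**1. Is Grade 3 hypoxia a DLT here?** Section 5.4.1 starts from every Grade 3 or 4 toxicity. Exceptions (a) to (j) cover pain, nausea and vomiting, fever, skin, metabolic/laboratory, neuropathy, hematologic, infusional reactions, fatigue or performance status, and infection. Hypoxia is absent, so a Grade 3 event is a DLT.

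**2. Dose after each successive event** (starting dose 6 mg/m², event graded 3):

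| Event | 10.2.3.4, first recovery under 1 hour | 10.2.3.4, first recovery over 1 hour | DLT rules |
|---|---|---|---|
| First | 100% = 6 | 50% = 3 | 50% = 3 |
| Second | 50% of prior = 3 | 50% of prior = 1.5 | 25% = 1.5 |
| Third | 50% of prior = 1.5 | off | stop |
| Fourth | off | – | – |

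The sections disagree only when the first event recovers in under an hour. With slower recovery they match. The event must also fall on Day 1 or 2, because after Day 3 no infusion is scheduled for the following day.

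**3. Size per affected subject.** The next infusion differs by 6 − 3 = 3 mg/m². The 3 mg/m² is a ceiling, since 10.1.1 also needs eligibility criteria met in time and FDA contact. Planned exposure is 3 courses × 3 days × 6 = 54 mg/m². If the event occurs at infusion k, there is no second event and every later dose is given, the cumulative difference is 3 × (9 − k):

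- k = 1 (Course 1 Day 1): 3 × 8 = 24 mg/m², or 24/54 = 44%.
- k = 8 (Course 3 Day 2): 3 × 1 = 3 mg/m², or 3/54 = 6%.

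**4. Is a Grade 3 event realistic at this dose?**

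- Phase I Table 1 lists "Hypoxia (1), Hypophosphatemia (3") among 6 subjects at 6.0 mg/m². That is 1/6, exact 95% CI 0.4% to 64%.
- Table 2 carries a row labelled "Transient hypoxia (grade 3") with one Course 1 entry at 6.0 and one Course 2 entry at 7.5 mg/m². The text of 1.3.5 instead reports "transient hypoxia (3 subjects"). The totals differ, but the count at 6.0 mg/m² in Course 1 is the same in both tables.
- The Overview reports no protocol-defined DLTs among 14 Phase II subjects at 6 mg/m². That is 0/14, exact 95% CI 0% to 23%. Whether its DLT definition matched this one is not stated.

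So Grade 3 hypoxia is plausible, but its frequency is poorly known. The documents do not say how many such events recovered within an hour.

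**5. Fatigue.** Take a treatment-related Grade 4 fatigue lasting 2 days or more, with performance status back to 2 or better inside a week. Section 10.2.6 permits 3 mg/m² next cycle; 5.4.4.1 withdraws the subject. For Grade 4 fatigue under 2 days with eligibility met, both give 50%. Section 1.3.5 says of Phase I "No Grade 4 toxicities were observed": 0/33, upper exact 95% limit 11%.

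**6. Neurotoxicity.** For Grade 3, the 50% in 10.2.4 agrees with the DLT rules. For related Grade 4, 5.4.4.1 withdraws the subject, while 10.2.4 gives a restart condition and a 50% dose without separating Grade 4.

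**The case against.** The strongest reply is that the general rule already governs. Section 10.1.1 covers every DLT, precedes 10.2 in the same chapter, and 5.4.3 states the reduction in bold. On that reading the full-dose restart applies only to desaturation that is not a DLT. A clinician who reads both sections would arrive at 50%. But the text contains no precedence statement, and the pointer used for hypotension and vascular leak is missing here. What the reply leaves standing is a missing limit in the section most likely to be consulted.

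The second reply is that saturation below 90% recovering within an hour may not be Grade 3. This stands as a limit. The documents do not give the CTCAE v3.0 criteria, and Phase I was graded on the NCI Common Toxicity Criteria. A reader might infer that every full-dose restart under 10.2.3.4 breaks the DLT rules; the documents do not support that.

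A hypoxic event might be classed as a brief infusional reaction under exception (h), but nothing in the text says so. Figure 1 is not shown. Its footnote 3 leaves a yes-or-no decision to the FDA, and footnote 4 supports 50%. Nothing more is claimed about it.

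On fatigue, 5.4.4.1 times the Grade 4 fatigue and 10.2.6 times recovery of performance status. A reader might infer a conflict window of 2 to under 7 days, but these are separate clocks and that window is not in the documents. Section 10.2.6 is also permissive, so obeying 5.4.4.1 breaks neither rule. The inconsistency remains for the case in step 5 of the working.

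On neurotoxicity, the 50% can be read as the dose if another course is given, and a withdrawn subject has none. A reader might count this as a third conflict; the text supports only an ambiguity.

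**Conclusion.** The point holds for hypoxia and is worth fixing. For a Grade 3 event on Day 1 or 2 that recovers in under an hour, the plan gives 6 mg/m² in one place and at most 3 mg/m² with FDA contact in others. This rests on the event being graded 3, which the documents make plausible from Phase I but do not establish for every saturation below 90%. The fatigue mismatch is real but secondary, and the neurotoxicity wording needs clarification only.

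A reader might turn the Phase I rate into an expected number of affected subjects among the 16. The documents do not support this: the share recovering within an hour is not given, and 1/6 has an interval from 0.4% to 64%. An average cumulative dose difference would likewise need equally likely event days and full later dosing, which nothing supports. The number affected is likely small. No endpoint, power or sample size is altered.

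**What to change.** - **10.2.3.4:** add a sentence such as *Grade 3 hypoxia is handled under Section 10.1 and Grade 4 under Section 5.4.4.1; the full-dose restart applies only below Grade 3.* If a full-dose restart after brief Grade 3 hypoxia is intended, list that event among the 5.4.3 exceptions with its time limit instead.
- **10.2.6:** for Grade 4 fatigue, add the 5.4.4.1 condition (under 2 days and eligibility criteria met).
- **10.2.4:** as a clarification, limit the 50% restart to Grade 3 and refer related Grade 4 events to 5.4.4.1.

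The cost is a wording amendment, with no added subjects, visits or tests. The downside is that a few subjects may receive a lower dose or be withdrawn when a clinician following Section 10.2 alone would have continued treatment.

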10.2.4 Neurotoxicity

Patients experiencing Grade 3 or worse neurotoxicity except confusion (i.e., objective peripheral neuropathy or prolonged weakness) for > 3 days (see Section 5.3.3f) will have treatment held. Treatment will not be restarted until that toxicity returns to \leq Grade 1. A dose reduction of 50% will be required for any subsequent course of treatment. In the event of Grade 3 or worse neurotoxicity, repeated neurological exams will be performed regularly, and documented, until symptoms resolve or irreversibility is documented.

10.2.5 Metabolic/laboratory

Symptomatic hyponatremia (sodium < 125 nmol/L, > 48 hours) or severe hyponatremia without symptoms (sodium < 120 nmol/L on 2 consecutive samples) will require permanent discontinuation of protocol therapy. Since asymptomatic hypophosphatemia was observed with relatively high frequency in our Phase II study of hu14.18-IL2 in adults with melanoma, all subjects due to receive this agent will be given oral phosphate supplementation prophylactically starting on day 1 and ending on day 8 of each course (see Section 10.3.4.3 for details). Intravenous phosphate supplementation will be considered in the event of symptomatic hypophosphatemia or persistent (> 24 hrs) asymptomatic hypophosphatemia (i.e., < 1.5 mg/dL) despite oral prophylaxis in order to prevent the serum phosphate from remaining < 2.0 mg/dL for > 48 hours. Glucose values greater than 250 mg/dL that are persistent for > 12 hours may be treated with parenteral insulin. If glucose values greater than 250 mg/dL are noted in the outpatient setting, the level will be rechecked within 24 hours, and appropriate management will be initiated.

10.2.6 Performance status

Treatment will be stopped for Grade 4 fatigue or an ECOG performance status of 4. If performance status improves to \leq 2 in < 1 week, fusion protein treatment dosing in the subsequent cycle can be restarted at 50% of the dose which caused this toxicity.

10.2.7 Temperature elevations

Fusion protein treatment will be held for persistent temperature elevations (> 6 hours) of 40° C or greater not responding to symptomatic treatment with antipyretics. Provided that renal function remains stable (i.e., creatinine does not increase more than 50% over baseline), all patients will receive indomethacin 25 mg/dose every 6 hours, starting 1 hour before the first dose of hu14.18-IL2 and continuing 12 hours after the last dose on day 3 (see premedication, Section 10.3.3). As most patients experience fevers, it is recommended to begin acetaminophen (325-650 mg) as soon as any elevated temperature (> 37.5° C) develops after the first dose of hu14.18-IL2, and to continue it on a scheduled basis for the next 60-72 hours (not to exceed 4 gm per day). Rigors, which may accompany temperature changes, can be treated with meperidine IV. Persistent temperature elevations > 39° C which are not well controlled with acetaminophen and indomethacin may also be treated with a cooling blanket. No dose modifications will be made for temperature elevations (unless the temperature persists > 40° C for > 6 hours) despite treatment with the above antipyretic approaches. If fever does persist for > 6 hours despite antipyretics, then hu14.18-IL2 treatment will be stopped. Treatment can be restarted within a 3-day course of treatment once the temperature is \leq 38° C. Treatment will then be at 50% of the dose which caused this toxicity.

Use of prophylactic antibiotics for fever:

Although the IL2 component of hu14.18-IL2 is known to, and expected to cause fever, IL2 is also known to cause some neutrophil dysfunction and predispose to bacterial infections, including central

catheter related infections. Thus, for fever $> 38.5^{\circ} \text{C}$, it is recommended that blood cultures be drawn, and a broad-spectrum antibiotic be considered if fever persists or the patient is clinically unstable.

10.2.8 Confusion

Confusion related to temperature elevations will be managed by aggressive use of antipyretics and cooling blankets, and will not require dose reduction or drug stoppage, if the confusion normalizes with initiation of aggressive antipyretic measures.

Persistent confusion (> 12 hours) which is clearly not temperature related or related to supportive care medicines (Benadryl, morphine, etc.) will require stopping study drug. Subsequent re-initiation of treatment at one-half the prior dose will proceed if reversal of this toxicity occurs prior to the next scheduled dose.

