5.4 Dose limiting toxicity and subsequent courses at reduced dose

5.4.1 Definition of DLT

The definition of DLT in this study differs from the standard definition. Dose-limiting toxicity (DLT) will be defined as Grade 3 or 4 toxicity, using the NCI Common Terminology Criteria for Adverse Events (CTCAE), version 3.0, EXCEPT as detailed below in Section 5.4.3. These toxicities will be evaluated for all subjects beginning on Course 1 day 1 during all courses of this study except for the time from the initiation of the surgical resection until recovery from surgery and initiation of Course 1 (for Group B) or Course 2 (for Group A) of protocol treatment.

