5.4.2 Clarification of need for exceptions for DLT determination

Since a secondary objective of this study is to evaluate adverse events associated with this experimental agent, careful documentation of toxicity (according to the NCI CTCAE version 3.0) is essential. Though the hu14.18-IL2 fusion protein is a relatively new molecule with modest clinical testing, it is derived from the human IL2 molecule and the humanized form of the ch14.18 chimeric antibody, both of which have had extensive clinical testing. Over the past 15 years of IL2 testing and 9 years of ch14.18 testing, certain side effects have been noted to occur frequently. These toxicities are generally transient, can be well controlled clinically and/or resolve spontaneously, and have no sequelae. Therefore, though some of these frequently seen side effects do score as Grade 3 or 4 toxicities, using the NCI CTCAE 3.0 scale, these toxicities have been excluded for determination of “dose-limiting toxicity” for both IL2 or ch14.18. The list of frequently seen toxicities below will therefore not be considered as dose limiting for the purposes of drug discontinuation, dose modification, or DLT determination for this study.

In order to evaluate the clinical anti-tumor activity and duration of response of hu14.18-IL2 in subjects with advanced melanoma, subjects enrolled in this clinical study will be treated at

6mg/M²/d, a dose below the MTD, as determined in our adult Phase I clinical trial and at a dose well tolerated (without DLT) in our recently completed Phase II trial.

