5.4.3 Detailed listing of DLT exceptions

The following toxicities will be graded and recorded, but will not be used as criteria for determining DLT:

- a) Grade 3 pain, requiring intravenous narcotics, provided that the narcotics are controlling the pain, and that IV narcotics for pain are not required > 48 hours after completion of hu14.18-IL2 on Day 3 of any treatment course;
- b) Grade 3 nausea and vomiting that resolves within 48 hours after completion of hu14.18-IL2 on Day 3 of any treatment course;
- c) Grade 3 fever (i.e., T > 40° C) lasting < 6 hours and controllable with antipyretics;
- d) Grade 3 skin toxicity that improves with treatment (e.g., IV Benadryl) within 24 hrs;
- e) Grade 3 metabolic/laboratory toxicity of hyponatremia, hyperglycemia, or hypophosphatemia in the absence of CNS symptoms and/or sequelae, that improves with or without treatment within 48 hrs;
- f) Grade 3 sensory or motor peripheral (non-cranial) neuropathy (i.e., interference with function plus objective weakness) if transient and reversing within 3 days of completion of hu14.18-IL2 of any treatment course. Subjective findings (e.g., tingling, hot/cold hands) are expected and will not be DLT;
- g) Grade 3 hematologic toxicity (or grade 4 lymphopenia – a known transient marker of immune activation by IL2) which improves to at least Grade 2 or pre-therapy baseline values without requiring transfusion within one week of completion of hu14.18-IL2 of any treatment course (see Section 10.2.1 for management of hematologic toxicity and transfusion guidelines);
- h) Grade 3 infusional reactions lasting less than 24 hours, readily controlled with supportive (non-steroidal) treatments (i.e., Benadryl) and not requiring epinephrine;
- i) Grade 3 fatigue or ECOG performance status that resolves in ≤ 1 week;
- j) Grade 3 infection that resolves in ≤ 1 week.

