The above dose limiting toxicity exceptions are based on the known, published, transient, reversible toxicities of IL2 and hu14.18. These toxicities may be expected, based on observations of hu14.18-IL2 given to 33 + 14 (phase I and II respectively) adults with melanoma, administered by the same schedule at similar doses to that being tested in this trial, and will not require interruption, modification, or discontinuation of treatment. In our experience with hu14.18-IL2 in adults with melanoma, asymptomatic hypophosphatemia is a relatively frequent occurrence. Therefore, all subjects scheduled to receive this agent will be given oral phosphate supplementation prophylactically starting on day 1 and ending on day 8 of each course (see Section 10.3.4.3 for details). **All grade 4 toxicities (except for transient lymphopenia) are considered as DLT and require stopping treatment with hu14.18-IL2. Following resolution of a DLT, and if subsequent hu14.18-IL2 treatment is given, it must be given at a reduced dose.**

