5.4.4 Treatment cessation/dose modification for DLT or significant non-DLT toxicity

Any subject demonstrating DLT or significant non-DLT toxicity (see Section 10.1.2) will require that treatment with the study agents be stopped. Depending upon the nature of the toxicity and its resolution, subjects will be considered for continued treatment at a reduced dose as described below (see also Figure 1). Any planned drug administration that is withheld due to DLT will not be given on a delayed schedule to “make up” for missed drug. All dose modifications are permanent.

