5.4.4.1 Dose-reduction plan for hu14.18-IL2

For toxicity associated with hu14.18-IL2, there must also be consideration of the schedule of administration. If this toxicity occurs on day 1 or 2 of any course, treatment can be resumed during that same course (i.e., on day 2 or 3) at 50% of the starting dose only if the toxicity has improved to meet eligibility criteria in time to give the day 2 or day 3 dose on schedule. If eligibility criteria are not met in time to receive additional therapy during the course in which the toxicity occurred, but are met in time to start the next course (i.e., day 1 of the next course +/- 7 days), treatment will resume at 50% of the dose that caused the DLT. If toxicity again requires treatment cessation, treatment can be restarted at 25% of initial treatment dose. If treatment at this reduced dose results in recurrence of DLT or significant non-DLT toxicity, treatment will be permanently discontinued.

Repeat lab testing will be done weekly until eligibility criteria are met, and treatment will begin at 50% of the prior dose. If after 4 additional weeks of testing, eligibility criteria still are not met, the subject will not be eligible for any additional treatment with the study agent responsible.

Subjects with Grade 4 toxicity related to protocol treatment (other than transient lymphopenia from hu14.18-IL2, see Section 5.3.3.g) will not receive additional protocol treatment during that treatment course. Patients experiencing Grade 4 neutropenia or leukopenia that lasts \leq 4 days; Grade 4 thrombocytopenia that can be corrected with platelet transfusion (see Section 10.2.1); or Grade 4 nausea, vomiting, anorexia or fatigue lasting less than 2 days, and resolves to meet eligibility criteria, may be eligible to receive continued study therapy (provided that all other criteria for continued treatment are met) at 50% of the dose received prior to the onset of this toxicity. Subjects with any other Grade 4 toxicity related to the protocol treatment will not receive additional protocol treatment during that course and will be withdrawn from the study. Subjects experiencing Grade 4 events that are clearly unrelated to the study treatment, last \leq 3 days, and improve to meet eligibility criteria, may be eligible to receive continued study therapy (provided that all other criteria for continued treatment are met) at 50% of the daily dose received prior to the onset of this toxicity.

[figure not shown]

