³ The “yes” or “no” will be based on the FDA’s decision after consulting with them on a case-by-case basis, both at the time of onset and time of resolution of the toxicity.

⁴ If this is the first time the DLT was noted, reduce dose to 50% of starting dose. If this is the second time the DLT was noted, reduce to 25% of starting dose. If this is the third time, treatment must stop—no further dose reductions are allowed.

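### Section 10.2.8 waives dose reduction and stoppage for fever-related confusion at any grade, while Sections 5.4 and 10.1.1 treat Grade 3 or 4 confusion as a DLT that stops treatment

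*Combined protocol and SAP*

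**What the plan says.** **The confusion rule.** Section 10.2.8 manages fever-related confusion with antipyretics and cooling blankets. It says that such confusion "will not require dose reduction or drug stoppage, if the confusion normalizes with initiation of aggressive antipyretic measures". No CTCAE grade appears. A second paragraph of 10.2.8 requires a stop for confusion lasting more than 12 hours that is clearly due neither to temperature nor to supportive medicines.

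**The DLT rules.**
- Section 5.4.1: "Dose-limiting toxicity (DLT) will be defined as Grade 3 or 4 toxicity", by CTCAE version 3.0, apart from the exceptions in 5.4.3.
- Section 5.4.2: the listed toxicities "will therefore not be considered as dose limiting for the purposes of drug discontinuation, dose modification, or DLT determination for this study". The list therefore decides dosing as well as classification.
- Section 5.4.3, items a to j: confusion is not named. Item c exempts Grade 3 fever "lasting < 6 hours and controllable with antipyretics".
- Section 5.4.3, closing paragraph: "All grade 4 toxicities (except for transient lymphopenia) are considered as DLT and require stopping treatment". Any later dose after a DLT must be reduced.
- Section 5.4.4: DLT or significant non-DLT toxicity "will require that treatment with the study agents be stopped".
- Section 5.4.4.1, after a short list of Grade 4 events that may allow re-treatment (confusion is not among them): "Subjects with any other Grade 4 toxicity related to the protocol treatment will not receive additional protocol treatment during that course". Such subjects are also withdrawn.
- Section 10.1.1 repeats the stop for any DLT and requires FDA contact before resuming at a reduced dose. Footnote 3 to Figure 1 makes a yes/no branch turn on the FDA's "decision after consulting with them on a case-by-case basis, both at the time of onset and time of resolution of the toxicity".

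**The neurotoxicity rule.** Section 10.2.4 holds treatment for Grade 3 or worse neurotoxicity lasting more than 3 days, and leaves confusion out of that hold.

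**The concern.** A physician facing Grade 3 confusion that clears with antipyretics finds two instructions. Section 10.2.8 allows the next infusion at full dose. Sections 5.4.4 and 10.1.1 require a stop, and make any resumption conditional on recovery, FDA contact and a lower dose. Infusions are given on three consecutive days, so the choice may have to be made by the next day.

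Either choice could be wrong. Following 10.2.8 could mean full-dose re-treatment after a DLT without the required FDA contact. Following 5.4 could mean a dose reduction that the authors did not intend, and 5.4.4 makes reductions permanent. What is at stake is an individual subject's dosing safeguard, not the trial's inference.

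**Working it through.** **Step 1. The same event under each rule.** The plan states no figure to reproduce. The event is fever-related confusion that normalizes with antipyretics at the starting dose of 6 mg/m², as a first DLT where it is one.

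| Grade | 10.2.8 as worded | 5.4.1-5.4.4.1 and 10.1.1 |
|---|---|---|
| 1-2 | No stop, 6 mg/m² | Not a DLT; physician discretion under 10.1.2 |
| 3 | No stop, 6 mg/m² | DLT: stop. If resumed: FDA contact and 0.5 × 6 = 3 mg/m². If not resumed: 0 |
| 4 | No stop, 6 mg/m² | DLT: stop. If related to treatment: no more in that course, and withdrawal |

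The two columns agree for Grade 1-2 and differ for Grade 3 and Grade 4. The stop is unconditional. FDA contact and the reduced dose apply only if treatment resumes.

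**Step 2. Does any 5.4.3 exception cover it?** Item c covers the fever, not confusion caused by it. Item f covers only peripheral, non-cranial neuropathy. Item h covers short infusional reactions controlled with non-steroidal support and does not name confusion. None is an explicit exception.

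**Step 3. How do comparable supportive-care rules avoid the problem?** Fever (10.2.7) has a matching item c, pain (10.2.9) has item a, and neuropathy (10.2.4) has item f. The hepatic rule (10.2.2) caps its waiver at Grade 2 and requires a stop at Grade 3. The confusion rule has neither a matching item nor a cap.

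**Step 4. Can the frequency be bounded?** The documents report no confusion with hu14.18-IL2. With zero events in n subjects, the one-sided 95% upper limit is 1 − 0.05^(1/n).
- All 33 Phase I adults: 1 − 0.05^(1/33) = 8.7%; × 16 = 1.4 expected subjects.
- Adding the 14 Phase II adults (n = 47): 1 − 0.05^(1/47) = 6.2%; × 16 = 1.0. This assumes none of the 14 had Grade 3 confusion. The documents say only that there were no protocol-defined DLTs, and do not give that study's definition.
- Only the 12 Phase I adults at 6.0 or 7.5 mg/m²: 1 − 0.05^(1/12) = 22%; × 16 = 3.5.

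The limit moves more than threefold with the choice of denominator. Of the 33, 21 were dosed below 6 mg/m² (3 + 6 + 6 + 6, Table 1), and only 19 had a second course, against three planned here. Table 2 also disagrees with the narrative in Section 1.3.5: it shows no fever above 40 °C and two hypoxia entries, while the narrative reports one and three subjects. These limits also refer to any Grade 3 confusion, not the fever-related subset. They do not give a usable ceiling.

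**Step 5. Does anything else in the plan change?** The Section 9.4.9 boundaries count Grade 4 events. Section 10.2.8 says nothing about DLT classification, so a Grade 4 confusion event counts there either way. No endpoint definition or sample-size input refers to confusion.

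**The case against.** The strongest reply is that 10.2.8 is the specific rule and was meant to govern. The carve-out of confusion in 10.2.4 points that way, and this stands as evidence of intent. It removes confusion only from the 10.2.4 hold, however. It does not add an exception to 5.4.3, and no visible sentence gives 10.2.8 precedence.

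The opposite harmonizing reading is also available: Section 10.2 is supportive care, so 10.2.8 could apply only below DLT level. That is reasonable, but 10.2.8 does not say so. A third reading records the event as an infusional reaction under item h. That too is the reader's inference.

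Three cautions stand. The documents do not reproduce the CTCAE grades for confusion, so how often confusion that clears with antipyretics would be graded 3 is unknown. Figure 1, cited by 5.4.4, is not visible apart from some footnotes, and might clarify the point. Inpatient infusion and the discretion in 10.1.2 reduce the risk, although 10.1.2 covers toxicity that is not a DLT, and whether this event is one is the question.

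A reader might infer from the absence of confusion in the 14.3 reporting exceptions that the authors did not mean to exempt it. The documents do not support that. Section 14.3 does not mirror 5.4.3: it omits Grade 3 peripheral neuropathy, which is a DLT exception, and includes hypotension, hepatic toxicity and capillary leak, which are not.

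**Conclusion.** The inconsistency is real in the visible text, and its severity is minor. Two operative dosing rules give different actions for the same event, and nothing visible ranks them. The practical difference at Grade 3 is 6 mg/m² against 3 mg/m² or no further infusion.

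A reader might go further in three ways that the documents do not support:
- **That the problem is confined to Grade 3.** The closing paragraph of 5.4.3 is explicit for Grade 4 and is the natural rule to follow, but 10.2.8 as worded excludes no grade. Where the boundary lies is a matter of reading.
- **That FDA contact and a reduced dose always follow.** They apply only if treatment resumes.
- **That at most about one subject in 16 could be affected.** A rate limit multiplied by 16 is an expected count, not a maximum, and the limit itself ranges from 6.2% to 22%.

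The conclusion assumes that Figure 1 and the unavailable text around it do not settle the point, and that some fever-related confusion that clears with antipyretics can reach Grade 3 under CTCAE version 3.0. No endpoint, sample size or Section 9.4.9 rule changes.

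**What to change.** **Preferred.** In 10.2.8, limit the waiver to Grade 1-2 fever-related confusion and refer Grade 3-4 to 5.4.4 and 10.1.1. In 10.2.4, add a pointer to 10.2.8 where confusion is carved out.

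**If the investigators intend to waive Grade 3.** Add to 5.4.3 an exception for Grade 3 fever-related confusion that resolves with antipyretics within a fixed time. The 6 hours in item c and the 12 hours in 10.2.8 are candidate limits. State in 10.2.8 that Grade 4 confusion always follows 5.4.3 and 5.4.4.1.

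Under either option, check that Figure 1 agrees.

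**Cost.** Protocol wording only. The preferred option may bring an occasional extra dose reduction and FDA contact. The alternative keeps full dosing, but a time limit must be chosen and full-dose re-treatment after a Grade 3 event accepted.
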